**Double-Blinded Randomized Prospective Trial of Intranasal Capsaicin Treatment for Non-
Allergic Irritant Rhinitis**

NCT02493257

Version Date: 11/18/2019

IRB NUMBER: HSC-MS-14-0173
IRB APPROVAL DATE: 11/18/2019

Protocol Title: Double-Blinded Randomized Prospective Trial of Intranasal Capsaicin Treatment for Non-Allergic Irritant Rhinitis

Principal Investigator: [name]

Co-Investigators: [name] PhD; [name]; [name]

Study Coordinator: [name] PhD

Population: The study population will consist of patients with non-allergic irritant rhinitis (NAIR) as defined by history (symptoms of nasal congestion, rhinorrhea, nasal itching or sneezing upon exposure to nasal irritants) and positive optical rhinometer (Rhinolux™, Rhios GmbH, and Germany) response with intranasal challenge with capsaicin. Participants will be sought from those presenting to the outpatient Otolaryngology clinic at the University of Texas Medical School at Houston. Patients included in the study will be between the ages of 18 and 70 with no history of sinonal surgery, intranasal steroid use for more than 4 weeks, intranasal or systemic antihistamine for 3 days, intranasal or systemic decongestants for 3 days, chronic rhinosinusitis, inflammatory or granulomatous diseases, asthma, allergic rhinitis, immunocompromised state or radiation to the head and neck.

Sample size: 11 participants will need to be recruited to each group (experimental and control) to detect a significant post-treatment change. In order to reach our target enrollment of 22 participants we expect to screen 60 subjects.

Number of sites: single site

Study duration: 13 weeks

Subject duration: 13 weeks

General Information: The proposed study seeks to investigate the effect of intranasal capsaicin treatment in patient with Non-allergic irritant rhinitis (NAIR), as well as evaluate optical rhinometry (ORM) as a means to quantify symptomatic improvement in NAIR patients during and after treatment.

Background Information:

Rhinitis is defined as inflammation of the membranes lining the nose, characterized by symptoms including itching, rhinorrhea, and/or nasal congestion. It is a common clinical illness throughout the world and is consistently ranked among the most frequent of chronic illnesses, significantly affecting the quality of life of patients and their families. Non-allergic rhinitis is defined as rhinitis symptoms in the absence of an identifiable allergy, structural abnormality, or sinus disease. Non-allergic irritant rhinitis (NAIR) affects as many as 17 million Americans, and approximately 22 million suffer a combination of allergic rhinitis (AR) and NAIR (1).

The pathophysiology of NAIR is largely unknown. It is described as a non-specific nasal hyper-reactivity that occurs on exposure to non-immunologic stimuli including changes in temperature, strong odors, and airborne irritants. Nasal mucosa is innervated by autonomic and

sensory neurons. Such stimulation of sensory fibers (C and A δ) can lead to the irritative effects including sneezing, itching, rhinorrhea, and pain (2). Such effects are believed to be mediated by the trigeminal system.

The trigeminal nerve fibers in the nasal cavity respond to a wide variety of chemical stimuli. One known receptor is the TRPV-1 vanilloid receptor. Capsaicin is one such ligand of the TRPV-1 receptor; however, the receptor is also activated by noxious temperatures and low extracellular pH (3). Stjarne et al showed that although capsaicin acts as an irritant in controls and rhinitic patients, those with NAIR reported increased rhinorrhea and nasal congestion (4). In animal studies, capsaicin has been shown to stimulate sensory C-fibers releasing substance P and calcitonin gene related peptide (CGRP), both potent vasodilators (5). However, repeated stimulation showed desensitization and degeneration of C-fibers (6), which is the basis for capsaicin usage in pain treatment.

Currently, intranasal steroids are the only FDA approved agents used in NAIR. Topical applications of capsaicin have been used in the treatment of pain particularly in post-herpetic neuralgia, post mastectomy pain, and hypersensitivity disorders of the lower urinary tract (7-9). LaCroix et al has shown that repeated administration of intranasal capsaicin decreased nasal symptoms in NAIR patients (10). Although multiple studies using intranasal capsaicin have been shown to improve nasal symptoms of NAIR patients (11-13); there have been no studies in which NAIR patients were objectively identified and symptom improvement was objectively monitored.

Optical rhinometry (ORM) has been proposed to be a useful instrument in the assessment of nasal blood flow, as an indirect measurement of nasal congestion (14). A positive correlation has been made between optical rhinometry and symptom scores for nasal congestion in nasal provocation testing (15). ORM has also been shown to correlate with changes in nasal cavity cross sectional area measured via acoustic rhinometry (16). In addition, our group recently reported that ORM following 0.05 mM capsaicin challenge can be utilized to identify NAIR patients (17).

A study by Lambert et. al. (2012) was able to objectively identify patients with NAIR by intranasal capsaicin challenge followed by assessment with optical rhinometry (17). Studies have shown that capsaicin therapy can improve symptoms of patients historically identified with NAIR via visual analog scale (VAS) rating of symptoms and symptom surveys; however, there has been no study evaluating the capsaicin therapy on patients objectively identified as NAIR patients.

Multiple studies have demonstrated that intranasal capsaicin can improve nasal symptoms of NAIR patients (11-13). Regarding the usage of capsaicin, there is a product on the market: Sinus Buster which has capsaicin as the active ingredient. Numerous research papers have evaluated the efficacy and safety of Sinus Buster for the treatment of congestion in non-allergic rhinitis patients (5, 12). However, the diagnosis of NAIR in these previous studies was based primarily on history. In addition, the primary outcome in these studies was symptomatic without any objective evaluation. The goal of this study will be two-fold: with patients objectively identified as NAIR patients via the optical rhinometer, we will re-evaluate the therapeutic action of intranasal capsaicin on the management of rhinitic symptoms. We expect that the patients will show significant improvement in their symptoms. We will then use optical rhinometry as a means to objectively monitor changes in symptoms in NAIR patients. We expect that post treatment, patients will no longer have the positive response previously seen on intranasal capsaicin challenge before receiving treatment. We hope to be able to establish optical

rhinometry as an objective measurement of symptom improvement for NAIR symptoms, along with the subjective patient surveys.

Objectives:

1. To establish optical rhinometry as an objective means of evaluating changes of NAIR symptoms after treatment.
2. To re-evaluate the therapeutic action of intranasal capsaicin on the management of rhinitic symptoms in objectively defined NAIR patients.

Study Design:

The study will consist of patients with non-allergic irritant rhinitis (NAIR) as defined by history (symptoms of nasal congestion, rhinorrhea, nasal itching or sneezing upon exposure to nasal irritants) and positive optical rhinometer (Rhinolux™, Rhios GmbH, and Germany) response with intranasal challenge with capsaicin (17). Participants will be sought from volunteers and those presenting to the outpatient Otolaryngology clinic at the University of Texas Medical School at Houston. Patients included in the study will be between the ages of 18 and 70 with no history of sinonasal surgery, intranasal steroid use for more than 4 weeks, intranasal or systemic antihistamine for 3 days, intranasal or systemic decongestants for 3 days, chronic rhinosinusitis, inflammatory or granulomatous diseases, asthma, allergic rhinitis, immunocompromised state or radiation to the head and neck.

Allergy Testing to Identify and Exclude Subjects with Allergic Rhinitis

All previously consented subjects with history consistent with NAIR will be screened with a skin prick test (Multi-Test II Lincoln Diagnostics, Decatur, IL USA) to 6 common allergens including dust mite, mixed mold extract, cat hair, grass pollen, insect extracts, and bermuda grass extract to exclude allergic rhinitis. Those with confirmed negative skin prick testing will be eligible for the study.

Capsaicin Challenge and Optical Rhinometry

The optical rhinometer apparatus is applied to either side of the nasal dorsum according to the manufacturer's instructions. A one-minute baseline recording will be obtained and averaged. Capsaicin solution (Sigma Chemical, St. Louis, MO USA) will be diluted in 1% ethanol vv and 0.9% normal saline. 1% ethanol in 0.9% normal saline will serve as the vehicle solution. A mucosal atomizer device (MAdomizer, Wolfe Tory Medical, Inc Salt Lake City, UT USA delivering a 100 μ l solution will be used to deliver a dose of capsaicin totaling 1.5 μ g of capsaicin (0.05 mM) to the anterior face of the inferior turbinate of each nare. The maximum change in optical density (OD) will be recorded. Patients with a maximum change in OD of at least 0.2 will be considered a positive response and included in the study.

A composite symptom score will be recorded based a commonly used rhinitis rating system as recommended by the FDA for clinical trial studies on allergic rhinitis (<http://www.fda.gov/downloads/Drugs/GuidanceComplianceRegulatoryInformation/Guidances/ucm071293.pdf>). Each of the following 4 symptoms: nasal itching/tingling, nasal congestion, sneezing and rhinorrhea, will be rated on a 0-3 scale of severity (Appendix B) and a summed composite score will be recorded for each subject.

Capsaicin Treatment Concentration

The capsaicin solution will be prepared by using the formula previously reported by Van Rijswijk et al; (0.1mmol/l) diluted in ethanol and 0.9% normal saline (19). Using the MAD, 0.8mL will be delivered to each nasal cavity for a total of 24.4 ug per nasal cavity.

Study Procedure:

[figure not shown]
There will be a total of 4 visits. On the first visit, patients will be consented and undergo skin prick testing, the capsaicin challenge and Optical Rhinometry. Prior to undergoing the capsaicin challenge, a composite symptom score will be recorded. Patients with confirmed negative skin prick testing, and positive response on ORM will be eligible for the study and will be asked to return for treatment. Those who are not eligible will not be responsible for any costs associated with screening and will be compensated for parking as well as \$25.00 for their time.

At the second visit, the NAIR patients will have been randomized and blinded into two groups: Group A will be treated with vehicle spray; and Group B will be treated with the capsaicin spray. The PI will be blinded to the treatment. A member of the research team, which consists of Drs. [name], [name], [name], and [name] (research coordinator), will assist during the randomization and distribution of appropriate pre-made medications so that the PI and subjects remain blinded.

5 consecutive applications of capsaicin or placebo will be administered intranasally, with 1 hour between each application. Fifteen minutes prior to each application of medication, the nasal mucosa will be anesthetized with 100 ul of 1% lidocaine will be applied to each nasal cavity via MAD for all study participants. The lidocaine should not alter the nasal mucosa reaction to capsaicin; and is meant to anesthetize the area from the mild stinging of capsaicin. In fact, because lidocaine has a very mild stinging sensation at times; it can serve to mask the stinging one may get with intranasal capsaicin. Using the MAD, 100 μ L of 1% ethanol in 0.9% saline solution (Group A) or 0.8 mL solution with (0.1mmol/l) of capsaicin in 1% ethanol in 0.9% saline (Group B) will be delivered to each nasal cavity. On this day, they will not need to undergo optical rhinometry. Patients will fill out composite symptoms scores before and five minutes after 1st and 5th treatments. Patients who complete this portion of the experiment will receive \$50 dollars in compensation as well as parking.

Patients will then follow up 4 and 12 weeks after initiating treatment. At the 4 week and 12 week follow-up appointments, subjects will undergo capsaicin challenge followed by ORM and composite symptom score of nasal symptoms will be reported. Patients who complete both follow up visits will receive \$25 dollars in compensation as well as parking.

Study Protocol

Compensation:

In summary, patients that undergo the screening process and complete the skin prick testing and intranasal capsaicin challenge and ORM will be compensated \$25 as well as parking validation. Patients that undergo the treatment will be compensated \$50 plus parking for completing that day. Patients that complete the study and return 4 and 12 weeks post treatment, will be compensated \$25 plus parking.

Data and Safety Monitoring:

Previous studies have shown that the concentration of capsaicin that will be used is generally well tolerated.

Regarding the lidocaine, it is administered routinely in our clinic prior to nasal endoscopy and flexible laryngoscopy exams. Side effects can include minor stinging and burning when applied to the nose. Because it is an intranasal spray, there is a risk that patients will swallow it and may have difficulty swallowing for up to 45 minutes after application. We express to patients that they should avoid eating or drinking anything up to 45 minutes after the lidocaine application.

Regarding skin prick testing, patients may have mild discomfort where the skin is pricked. They may have symptoms such as itching, a stuffy nose, red watery eyes, or a skin rash. Rarely, people can have anaphylaxis, but this usually only occurs with intradermal testing, which we will not be performing. If patients become short of breath, we do have oxygen available in the clinic.

Patients will be educated to call the outpatient Otolaryngology clinic at the University of Texas Medical School at Houston if there are any adverse effects.

Human Subjects:

Participants will be sought from those presenting to the outpatient Otolaryngology clinic at the University of Texas Medical School at Houston. Patients included in the study will be between the ages of 18 and 70 with no history of sinonasal surgery, intranasal steroid use for more than 4 weeks, intranasal or systemic antihistamine for 3 days, intranasal or systemic decongestants for 3 days, chronic rhinosinusitis, inflammatory or granulomatous diseases, asthma, allergic rhinitis, immunocompromised state or radiation to the head and neck.

This is a small study of only 22 subjects total and as addressed previously we anticipate screening 60 subjects in order to complete our enrollment. . Our practice consists of adult patients with a majority of who speak and read English. Therefore, it is unlikely to exclude a subject from the study because they do not speak or read English

Statistical Analysis:

Justification of sample size:

Using [name] paper (17) : his article showed the average maximum optical density in NAIR patients was 0.2 (SD 0.051), seen when using the 0.05 mM concentration of capsaicin during the capsaicin challenge and ORM. Healthy control subjects had a mean maximal OD change of 0.174 (SD 0.034). This was significant to $p=0.01$. Based on this data, 11 patients will need to be recruited to detect a significant post-treatment change.

Student's t-test will be used to compare the mean change in composite symptom scores pre and post-treatment in both groups. Student's t-test will also be used to compare changes in maximal optical density in response to capsaicin challenge pre- and post-treatment in both

groups. Statistical significance will result if $p < 0.05$. The Spearman Rank Correlation will be used to analyze associations between composite symptom scores and changes in OD.

Ethics:

IRB approval will be sought from CPHS

Data Handling and Record Keeping: In order to maintain confidentiality, a data sheet with patient's names and data collected for the study (see data sheet) will be stored in a locked file cabinet within the department of Otorhinolaryngology. Access to data sheets in patient will be limited to co-investigators and research coordinator. Only de-identified data or collective data will be shared.

Quality control and assurance: In order to confirm that the diagnosis of non-allergic irritant rhinitis is accurate and made in an unbiased manner, a history of rhinitic symptoms will be confirmed with objective skin testing.

All datasheets will be recorded by PI and reviewed by at least one of the other 3 co-investigators to ensure accuracy in the recording of clinical data.

Publication Plan: This study has been funded by the American Association of Otolaryngic Allergy (AAOA) Foundation Grant. Results from this study will be presented at a future AAOA national meeting and initial publication rights will be given to the International Forum of Allergy and Rhinology.

All enrolled subjects will be notified of any publication resulting from this study, but these publications will present data on only the aggregate group.

REFERENCES

2. Hummel T. Assessment of intranasal trigeminal function. *Int J Psychophysiol*. 2000 May;36(2):147-55.

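### Patients enter on one OD reading at or above the plan's own NAIR mean, so OD will drift down on retest without treatment; the OD effect should be tested only as capsaicin versus vehicle

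*Combined protocol and SAP*

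**What the plan says.** **Entry.** Study Design, Capsaicin Challenge and Optical Rhinometry: "Patients with a maximum change in OD of at least 0.2 will be considered a positive response and included in the study". The reading comes from one challenge at the first visit (Study Procedure). Entry also needs a history of NAIR and a negative skin prick test.

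**Planning figures.** Statistical Analysis, Justification of sample size, citing an earlier study that used the same 0.05 mM challenge: "the average maximum optical density in NAIR patients was 0.2 (SD 0.051"), and "Healthy control subjects had a mean maximal OD change of 0.174 (SD 0.034").

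**Expectation.** End of Background Information: "We expect that post treatment, patients will no longer have the positive response previously seen on intranasal capsaicin challenge before receiving treatment". No comparator is named.

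**Retest and analysis.** Both randomised groups, vehicle (A) and capsaicin (B), repeat the challenge at weeks 4 and 12. The Statistical Analysis section plans a Student's t-test on changes in maximal OD from before to after treatment in both groups. It does not say whether the comparison is within each group or between them. The sample size statement is also framed around change after treatment and not a difference between groups: "11 participants will need to be recruited to each group (experimental and control) to detect a significant post-treatment change".

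**The concern.** The entry cut-off is the plan's stated NAIR mean. On those figures about half of NAIR patients qualify on any one reading, and some of them do so because that reading happened to be high. Their next reading will on average be closer to 0.2, and some will fall below it, whatever they were sprayed with.

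The vehicle arm is there to absorb this, but only if the two arms are compared. Two parts of the plan leave another reading open: the expectation that patients will stop being positive, and the pre/post wording of the OD t-test. Either would let ordinary retest drift in Group B count as a capsaicin effect. It would also count in favour of the first objective, which is to establish optical rhinometry as an objective measure of change after treatment.

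**Working it through.** **Inputs from the documents.** Cut-off 0.2; NAIR mean 0.2, SD 0.051; healthy-control mean 0.174, SD 0.034; 11 per group; significance level 0.05 (taken as two-sided, which the plan does not state).

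**Assumptions.** OD change is normally distributed; the NAIR mean is exactly 0.200; the SD is the same at retest; the test-retest correlation r is 0.9, 0.7 or 0.5. The documents give no r.

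**The plan's own figure.** The 11 per group is stated without power, target effect or SD of change. A two-sample, two-sided t-test at 80% power on the quoted figures (difference 0.026, pooled SD √[(0.051² + 0.034²)/2] = 0.0433) needs 45 per group. That is a separate matter. Here 11 is taken as given, and nothing below depends on how it was reached.

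**1. Share at or above the cut-off on one reading.**
- NAIR: 1 − Φ((0.2 − 0.2)/0.051) = 50%.
- Healthy controls: 1 − Φ((0.2 − 0.174)/0.034) = 1 − Φ(0.765) = 22%.

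**2. Mean at entry among those selected.** 0.2 + 0.051 × φ(0)/0.5 = 0.2 + 0.051 × 0.798 = 0.241.

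**3. Drift with no treatment effect.** Expected fall = (1 − r) × 0.0407. Because the cut-off sits at the mean, the chance of falling below 0.2 at one retest is arccos(r)/π.

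**4. False-positive rate of a within-arm test.** Simulation of 11 patients selected at OD ≥ 0.2, retested with no treatment effect, and analysed by a paired t-test.

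| Assumed r | Average fall in OD | Untreated loss of positivity | Expected number of 11 | Within-arm test significant |
|---|---|---|---|---|
| 0.9 | 0.004 | 14% | 1.6 | about 8% |
| 0.7 | 0.012 | 25% | 2.8 | about 16% |
| 0.5 | 0.020 | 33% | 3.7 | about 25% |

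A between-arm t-test on change in the same simulated setting stays at about 5%. For scale, the NAIR-control difference in the planning data is 0.200 − 0.174 = 0.026.

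**5. Sensitivity to rounding.** The NAIR mean is printed to one decimal. For r from 0.9 to 0.5, untreated loss is:
- 16% to 36% if the true mean is 0.195;
- 13% to 31% at 0.205;
- 10% to 24% at 0.220;
- 5% to 12% at 0.249.

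**6. The expectation under full normalisation.** This step needs no r. If treatment moved every patient to the healthy-control distribution, 22% would still be positive: 11 × 0.222 = 2.4 patients. The chance that all 11 would be negative is 0.778¹¹ = 6%.

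**The case against.** The strongest reply is that the design already deals with retest drift. Patients are randomised and blinded against vehicle, both arms are re-challenged at the same weeks, and regression to the mean is expected equally in both. The planned variable is continuous OD change; loss of positivity is an expectation in the Background and not a defined endpoint. All of this stands. It means the between-arm comparison is sound. It does not mean the plan has committed to that comparison, and its wording leaves a within-arm test open.

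The size of the drift depends on an r that the documents do not give, and it is smaller if 0.2 was rounded down from a higher mean. That also stands, so the figures are conditional. The direction is not: some drift follows for any r below 1.

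The 22% still positive assumes that treated patients come to resemble healthy controls. The Background describes desensitisation and degeneration of C-fibres, so responses below the healthy level are possible and fewer than 22% might remain positive.

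A reader might also infer that the patients are not objectively identified, or that the challenge adds little to history and skin test. The documents do not support either. The 22% is for healthy controls; no OD distribution is given for history-positive, skin-test-negative people without NAIR, which is the comparison needed. A sensitivity of 50% means cases missed at screening, not people wrongly enrolled.

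**Conclusion.** The point holds, within limits. On the plan's own figures the cut-off equals the NAIR mean, so patients chosen on one reading will drift toward 0.2 untreated. Under normality and a mean of exactly 0.200, the fall is 0.004 to 0.020 and loss of positivity 14% to 33% for assumed r of 0.9 to 0.5. If OD change is tested within an arm, the error rate rises from 5% to between about 8% and 25%. If it is tested between arms, there is no bias.

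The defect is therefore one of specification: the plan does not say which comparison counts, and its stated expectation has no comparator. The cut-off need not move, and the entry definition is not invalidated. Any mention of 50% sensitivity or 78% specificity should be labelled as derived from summary means and SDs under normality, with specificity against healthy controls; they are not observed accuracy.

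**What to change.** Keep the 0.2 entry rule and change the wording in two places.

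- **Statistical Analysis.** State that the test of OD effect is the Group B minus Group A difference in change in maximal OD from baseline, at weeks 4 and 12. State that within-arm change, or loss of a positive response within an arm, is not evidence of efficacy. Report the number losing positivity in both arms descriptively, with the between-arm difference and its confidence interval.
- **Background Information.** Reword the expectation as a difference from vehicle instead of the disappearance of positive responses in treated patients.

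The cost is a few sentences, one small table and a more modest claim. No visit, procedure or entry criterion changes.

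### The symptom score is fixed before the capsaicin challenge at visit 1 but listed after it at weeks 4 and 12, so the change score may compare an unprovoked baseline with a provoked follow-up

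*Combined protocol and SAP*

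**What the plan says.** All places are in the combined protocol and SAP.

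- **Study Procedure, visit 1:** "Prior to undergoing the capsaicin challenge, a composite symptom score will be recorded".
- **Study Procedure, visit 2 (treatment day, no ORM needed):** "Patients will fill out composite symptoms scores before and five minutes after 1st and 5th treatments".
- **Study Procedure, weeks 4 and 12:** "subjects will undergo capsaicin challenge followed by ORM and composite symptom score of nasal symptoms will be reported". No time relative to the challenge is given for the score.
- **Capsaicin Challenge and Optical Rhinometry:** the score sums four symptoms (itching/tingling, congestion, sneezing, rhinorrhea), each rated 0 to 3, so it runs from 0 to 4 × 3 = 12. Neither a time point nor a recall period is stated there.
- **Statistical Analysis:** Student's t-test will "compare the mean change in composite symptom scores pre and post-treatment in both groups". The visits and time points that count as pre and post are not named. Also: "The Spearman Rank Correlation will be used to analyze associations between composite symptom scores and changes in OD".

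**The concern.** The protocol's own background gives reason to think that timing matters. On capsaicin exposure it reports that "although capsaicin acts as an irritant in controls and rhinitic patients, those with NAIR reported increased rhinorrhea and nasal congestion"; those are two of the four scored items. It also says: "A positive correlation has been made between optical rhinometry and symptom scores for nasal congestion in nasal provocation testing". Enrolment requires an optical density (OD) change of 0.2 or more on this same challenge, so the sample is selected for reacting to it.

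A score taken minutes after the challenge may therefore measure something different from one taken before it. Objective 2, the effect on rhinitic symptoms, rests on the change in this score. If the baseline is at rest and the follow-up is provoked, the change contains the challenge reaction as well as the treatment effect. The Spearman analysis has a related but secondary problem. The OD response is always provoked, whereas the score would be unprovoked at visit 1 and provoked at weeks 4 and 12, and the plan does not say which score enters.

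**Working it through.** The plan states no figure on this point to reproduce. Its sample size of 11 per group rests on OD data and does not bear on score timing. The check is a comparison of the text, followed by algebra with assumed inputs.

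**Step 1. Timing by visit**

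| Visit | Challenge that day | Stated timing of the score |
|---|---|---|
| 1 | yes | before the challenge |
| 2 | no | before and after the 1st and 5th applications |
| Weeks 4 and 12 | yes | none relative to the challenge; named last |

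Timing is specified at visits 1 and 2 and left open at the two visits that supply the follow-up data. Both candidate baselines (visit 1, and visit 2 before the first application) are unprovoked by the challenge.

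**Step 2. Effect on the change score if the follow-up order is taken literally**

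Assumed quantities, none of them in the documents:
- c = points that a challenge adds to the score
- b = share of c that treatment removes (0 to 1)
- d = true effect of capsaicin on the resting score, with no resting change on vehicle

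Then:
- vehicle change = c
- capsaicin change = d + (1 − b)c
- arm difference = d + (1 − b)c − c = d − bc

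With d = −2, c from 1 to 3 and b from 0 to 1:
- vehicle reads +1 to +3, although nothing changed at rest
- capsaicin reads from −2 (b = 1) to −2 + 3 = +1 (c = 3, b = 0), although resting symptoms improved by 2; with c = 2 and b = 0 it reads −2 + 2 = 0
- the arm difference reads from −2 (b = 0) to −2 − 3 = −5 (c = 3, b = 1)

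If both scores were taken before the challenge, c would drop out: vehicle 0, capsaicin −2, difference −2.

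**Step 3. Which comparison is affected**

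- *Within group:* the change is shifted upwards, towards worsening, by c or (1 − b)c.
- *Between arms:* if treatment does nothing (d = 0, b = 0), the difference is 0 and the test keeps its level. If b is above 0, the estimate is d − bc, a mixture. The protocol expects b to be above 0 at least for the ORM response: after treatment, "patients will no longer have the positive response previously seen on intranasal capsaicin challenge before receiving treatment". That provoked symptoms fall with it is a further assumption.

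**Step 4. Rejection probabilities, as illustration only**

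Set d = 0, 11 per arm, two-sided 0.05, normal changes, noncentral t, probability in the stated direction.

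| Assumed shift (SD of change) | Between arms, favours capsaicin (shift = bc; df 20, nc = k√(11/2)) | Within group, shows worsening (df 10, nc = k√11) |
|---|---|---|
| 0 | 0.025 | 0.025 |
| 0.25 | 0.081 | 0.114 |
| 0.5 | 0.200 | 0.323 |
| 1 | 0.607 | 0.848 |

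These figures describe the shift k that was chosen. No SD of the change score is given, so the point scale of Step 2 cannot be tied to the SD scale here.

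**The case against.** The strongest reply is that sentence order in this protocol is not time order. At visit 1 the challenge and ORM are also mentioned before the score, yet the score is explicitly taken first. ORM itself starts with a one-minute baseline recording before capsaicin is given, so even the challenge-then-ORM wording is not a strict chronology. The final clause of the follow-up sentence can be read as one more item in a list, and a site could simply carry the visit 1 rule forward. The procedure figure, Appendix B and the data sheet might settle the matter. This stands: a reader might infer that the protocol orders scoring after the challenge, and the documents do not establish that. What remains is that the visible text permits either timing, possibly differing between patients or visits.

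Second, no recall period is given. If the form asks about a preceding period, a challenge minutes earlier may matter little. That also stands as a possibility, though scoring five minutes after an application at visit 2 suggests that the score is meant to reflect the present state.

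Third, a reader might conclude that an arm difference from provoked scores would be a false positive. That goes too far. Equal timing in both arms keeps the between-arm test valid under no effect. The protocol also describes the disease as nasal hyper-reactivity and defines patients by symptoms on exposure to irritants, so a blunted reaction to capsaicin is close to the disease feature, not plainly an artefact. The difficulty is one of interpretation: the estimate would not separate the two components. If provoked symptoms are the intended target, the baseline should be provoked as well.

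Fourth, the within-group shift runs against benefit, so it would not by itself create a claim of improvement. That is correct; the risk there is a missed improvement.

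**Conclusion.** The point holds as a timing gap that should be fixed, with medium confidence. The visit 1 score is fixed before the challenge; the week 4 and week 12 score is named after challenge and ORM and is not required beforehand. Taken in that order, the change score compares an unprovoked baseline with a provoked follow-up. This rests on the inferred order and on the challenge raising the score, for which the background gives direction but no size.

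The consequence depends on the test, and Statistical Analysis can be read either way. A within-group test is biased towards worsening. A between-arm test is valid under no effect, but estimates a mixture of resting symptoms and challenge reaction. The amount cannot be computed from the documents. In particular, the 0.607 and 0.848 in the working are not error rates of this trial; they follow from an assumed shift of 1 SD. The Spearman point is secondary, because the plan does not say which visits' scores are correlated.

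**What to change.** - **Study Procedure, follow-up visits:** state that at weeks 4 and 12 the four-item composite score is recorded immediately before the capsaicin challenge, as at visit 1.
- **Statistical Analysis:** name the visit 1 pre-challenge score as pre, and the week 4 and week 12 pre-challenge scores as post. Choosing visit 1 also avoids the visit 2 score, whose order relative to lidocaine is not stated.
- **Statistical Analysis:** state which score enters the Spearman correlation with OD change.

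If the figure, Appendix B or the data sheet already sets the time, copy it into the text and check that it agrees.

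The cost is one sentence in the procedure and two in the analysis section, with no added visit, form or patient. The downside is that the follow-up score would no longer capture symptoms provoked by the challenge, which the Spearman analysis might want. A second score after the challenge would recover them; it is optional, and would need to be taken at visit 1 too if a provoked change is to be analysed. Timing is best settled before the visits take place, since a pre-challenge score that was not taken cannot be obtained later.
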